9.2. Efficacy

9.2.1. Evaluations

9.2.1.1. Hospital Recovery Scale Assessment

The hospital recovery scale assesses a subject's clinical status and will be assessed as the subject's condition on Day 6 as the primary endpoint. The hospital recovery scale will be assessed on Days 2 to 14 (excluding the primary time point) as secondary endpoints.

The hospital recovery scale provides 6 mutually exclusive conditions ordered from best to worst, and the score reflects the subject's worst situation on the day of assessment:

1. Not Hospitalized
2. Non-ICU Hospitalization, Not Requiring Supplemental Oxygen
3. Non-ICU Hospitalization, Requiring Supplemental Oxygen
4. Admitted to the ICU, Not Requiring Invasive Mechanical Ventilation
5. Requiring Invasive Mechanical Ventilation
6. Death

The hospital recovery scale categories are defined below. For ease of categorization, the categories are defined from worst to best.

Hospital Recovery Scale: Definitions^a

6. Death
 - Subject died at any time on the day of assessment or earlier (all-cause mortality).
5. Requiring invasive mechanical ventilation
 - Any oxygen support requiring intubation or extracorporeal oxygenation
 - Invasive mechanical ventilation is used at any time on the day of assessment.
4. Admitted to the ICU, not requiring invasive mechanical ventilation
 - Subject met either of the 2 following criteria:
 - In the ICU (and ICU level of care is required during the day of assessment)
 - On the hospital ward, with or without supplemental oxygen, but deemed to require ICU level of care at any time during the day of assessment (eg, not transferred to ICU due to bed availability)
 - Requiring ICU level of care is defined by:
 - Some specific conditions:
 - Treatment of acute unstable arrhythmias
 - Treatment of complicated acid-base or electrolyte imbalances
 - Large volume resuscitation
 - Utilization of intravenous vasoactive medications

^a If a subject was discharged from the hospital “Against Medical Advice” on the day prior to the day of assessment, the subject will be categorized per the definitions above in the category the subject was in at the moment of discharge “Against Medical Advice”. The hospital recovery scale category will be considered missing on subsequent days.

If a subject declines medically-indicated mechanical ventilation or care that requires an ICU level of intervention, the subject will be categorized according to the care they would otherwise have received on that day.

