- Non-ICU hospitalized on the day of assessment (including readmittance), not ready for discharge during the whole day of assessment, as judged by the investigator and supplemental oxygen is required by the subject
- In the ICU but there is no medical reason to be in the ICU during the day of assessment, and supplemental oxygen is required by the subject

Requiring supplemental oxygen is defined by:

- Receiving supplemental oxygen through a face mask or nasal cannula and not being able to sustain a blood oxygen saturation of $\geq 94\%$ when breathing room air for 15 minutes at any time on the day of assessment.
- If supplemental oxygen was provided chronically pre-influenza infection (based on medical history), that amount of supplemental oxygen is exceeded to prevent hypoxia, tachypnea or dyspnea at some point on the day of assessment.
- Not receiving supplemental oxygen and either:
 - Having a blood oxygen saturation of $< 94\%$ when breathing room air for 15 minutes at any measurement on the day of assessment, or
 - In case of known pre-influenza $SpO_2 < 94\%$ (e.g., due to COPD), the current blood oxygen saturation on room air is lower than pre-influenza infection levels by at least 3%.

2. Non-ICU hospitalization, not requiring supplemental oxygen

Subject met either of the 2 following criteria:

- Non-ICU hospitalized on the day of assessment (including readmittance) and not ready for discharge during the whole day of assessment, as judged by the investigator
- In the ICU but there is no medical reason to be in the ICU during the day of assessment

1. Not hospitalized

Any of the following:

- Discharged from the hospital before the day of assessment
- Hospitalized at the day of assessment but ready for discharge on both the day of assessment and the day prior, as judged by the investigator (e.g., in case of lack of bed availability in a skilled nursing facility, lack of social support at home).

Notes: If a subject was discharged from the hospital “Against Medical Advice” on the day prior to the day of assessment, the subject will be considered as hospitalized (evaluating the other aspects of the HRS to define the correct category based on available data, e.g.: requiring supplemental oxygen, on the day of assessment). The hospital recovery scale category will be considered missing on subsequent days.

The HRS will be missing after a subject withdrew (except for withdrawal due to death) from the study.

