5. Requiring invasive mechanical ventilation;

When CMSTDTC<=(date of assessment) <=CMENDTC where CMADMTP="INVASIVE MECHANICAL VENTILATION"

And CMADMDS in ('Through Endotracheal tube' 'Through Tracheostomy tube' or 'Through ECMO')

4. Admitted to the ICU;

From the HO data set:

hostdy <=(day of assessment)<=hoendy
hoterm = 'ICU'

From the SS data set:

SSTESTCD= 'REQICU' and SSSTRESC='Y'
Or SSTESTCD= 'REASICU' and SSSTRESC='Y'
Or both REQICU and REASICU is missing and NOT (RDISHOSP = 'Y' on the day of assessment and RDISHOSP = 'Y' on the day (baseline visit) before)

OR

From the HO data set:

hostdy <=(day of assessment)<=hoendy
hoterm = 'WARD'

From the SS data set:

SSTESTCD='REASICU' and SSSTRESC='Y'
OR
SSTESTCD='REQICU' and SSSTRESC='Y'

3. Non-ICU hospitalization, requiring supplemental oxygen

Non-ICU hospitalization:

hostdy <=(day of assessment)<=hoendy
hoterm = 'Hospital inpatient Department (WARD)'
NOT (RDISHOSP='Y' on the day of assessment and RDISHOSP='Y' on day(baseline visit) before)

OR

hostdy <=(day of assessment)<=hoendy
hoterm = 'ICU'
NOT (RDISHOSP='Y' on the day of assessment and RDISHOSP='Y' on day(baseline visit) before)

OR

(day of assessment)=hoendy+1
RDISHOSP='N' on day(baseline visit) before

OR

In case re-hospitalization occurred (there is a day between the HOENDY of the previous record and HOSTDY of the next record)
(day of assessment) =HOSTDY (of the re-hospitalization)
NOT (RDISHOSP='Y' on the day of assessment and RDISHOSP='Y' on day(baseline visit) before)

AND

Requiring supplemental oxygen:

'Receiving supplemental oxygen through a face mask or nasal cannula and not being able to sustain a blood oxygen saturation of $\geq 94\%$ when breathing room air for 15 minutes at any time on the day of assessment.'

FAOBJ=CHRONIC OXYGEN USE and FAORRES='N'

CMADMTP in ("Non-Invasive Mechanical Ventilation", "Nasal Cannula", "Venturi Mask", "Simple Face Mask", "Nonrebreathing Face Mask with Reservoir and One-Way Valve".)

CMTRT=SUPPLEMENTAL OXYGEN and CMSTDTC <= date of assessment <= CMENDTC

VSOXYSAT in ('N' 'NA') at any time during the day of assessment (OR is missing)

OR

'If supplemental oxygen was provided chronically pre-influenza infection (based on medical history), that amount of supplemental oxygen is exceeded to prevent hypoxia, tachypnea or dyspnea at some point on the day of assessment.'

FAOBJ=CHRONIC OXYGEN USE and FAORRES='Y'

CMARTN = 'N'

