CMADMTP in ("Non-Invasive Mechanical Ventilation", "Nasal Cannula", "Venturi Mask", "Simple Face Mask", "Nonrebreathing Face Mask with Reservoir and One-Way Valve".) and CMTRT=SUPPLEMENTAL OXYGEN and CMSTDTC <= date of assessment <= CMENDTC

OR

'Not receiving supplemental oxygen and Having a blood oxygen saturation of <94% when breathing room air for 15 minutes at any measurement on the day of assessment'

No record in cm with oxygen supplementation

VSOXYSAT='N' at any time on the day of assessment OR [VSTESTCD='OXYSAT' and VSORRES<94% and VSOXSMRA='Y']

OR

'Not receiving supplemental oxygen and in case of known pre-influenza SpO2 <94% (eg, due to COPD), the current blood oxygen saturation on room air is lower than pre-influenza infection levels by at least 3%.'

No record in cm with oxygen supplementation

VSEVINTX= PRE-INFLUENZA INFECTION and VSTESTCD='OXYSAT' and 'VSORRES<94% and VSRMAIR='Y'

VSORRES and VSTESTCD=OXYSAT (of day of assessment) < [VSORRES and VSEVINTX= PRE-INFLUENZA INFECTION and VSTESTCD='OXYSAT' and VSRMAIR='Y' - 3]

2. Non-ICU hospitalization, not requiring supplemental oxygen

hostdy <=(day of assessment)<=hoendy

hoterm = 'Hospital inpatient Department (WARD)'

NOT (RDISHOSP='Y' on the day of assessment and RDISHOSP='Y' on day(baseline visit) before)

hostdy <=(day of assessment)<=hoendy

hoterm = 'ICU'

NOT (RDISHOSP='Y' on the day of assessment and RDISHOSP='Y' on day(baseline visit) before)

OR

(day of assessment)=hoendy+1

RDISHOSP='N' on day(baseline visit) before

OR

In case re-hospitalization occurred (there is a day between the HOENDY of the previous record and HOSTDY of the next record)

(day of assessment) =HOSTDY (of the re-hospitalization)

NOT (RDISHOSP='Y' on the day of assessment and RDISHOSP='Y' on day(baseline visit) before)

1. Not hospitalized

Some examples

Discharge against medical advice

If a subject is discharged 'against medical advice' on the day prior to the day of assessment, the subject will be considered as hospitalized (evaluating the others aspects of the HRS to define the correct category, e.g.: requiring supplemental oxygen, on the day of assessment)

We have a discharged against medical advice if on the day the subject is discharged (according to the HO dataset) the investigator indicated he is not ready and his SS status is discharged,

	Day 3	Day 4	Day 5	Day 6	Day 7	Day 8
Status (HO)	Hospitalized	Hospitalized	Hospitalized	Discharged	Home	Home
Case 1						

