ready (SS)	Not ready	Not ready	Not ready	Not ready	--	--
Status(SS)	hospitalized	hospitalized	hospitalized	Hospitalized	discharged	--
Against medical advice?					NO	
HRS	>1	>1	>1	>1	>1	HOME
Case 2						
ready (SS)	Not ready	Not ready	Not ready	Not ready	Ready	--
Status(SS)	hospitalized	hospitalized	hospitalized	Hospitalized	discharged	--
Against medical advice?					NO	
HRS	>1	>1	>1	>1	>1	HOME
Case 3						
ready (SS)	Not ready	Not ready	Not ready	Not ready	Not ready	--
Status(SS)	hospitalized	hospitalized	hospitalized	Hospitalized	discharged	--
Against medical advice?					NO	
HRS	>1	>1	>1	>1	>1	HOME
Case 4						
ready (SS)	Not ready	Not ready	Not ready	Not ready		--
Status(SS)	hospitalized	hospitalized	hospitalized	Discharged		

Against medical advice?				YES		
HRS	>1	>1	>1	>1	>1	Missing
Case 5						
ready (SS)	Not ready	Not ready	Not ready	Ready	--	--
Status(SS)	hospitalized	hospitalized	hospitalized	discharged		
Against medical advice?				NO		
HRS	>1	>1	>1	>1	HOME	HOME
Case 6						
ready (SS)	Not ready	Not ready	Not ready	Ready	--	--
Status(SS)	hospitalized	hospitalized	hospitalized	hospitalized	discharged	
Against medical advice?				NO		
HRS	>1	>1	>1	>1	HOME	HOME
Case 7						
ready (SS)	Not ready	Not ready	Ready	Ready	--	--
Status(SS)	hospitalized	hospitalized	hospitalized	hospitalized	discharged	
Against medical advice?				NO		
HRS	>1	>1	>1	HOME	HOME	HOME
Case 8						
ready (SS)	Not ready	Not ready	Not ready	--	--	--
Status(SS)	hospitalized	hospitalized	discharged	--	--	
Against medical advice?			NO			
HRS	>1	>1	>1	>1	HOME	HOME

Only in case 4 above we have a discharge against medical advice which would lead to missing values from day 8 onwards. The HRS on day 7 is defined by the other aspects of the HRS (requiring oxygen, ICU,..) on day 7 and not copied from day 6.

Requiring supplemental oxygen

	Case 1	Case 2	Case 3	Case 4	Case 5	Case 6
supplemental oxygen (CM)	YES	YES	NO	NO	NO	NO
Chronic oxygen use	No	yes	Not used	Not used	Not used	Not used
returned to prior level?	Not used	N	Not used	Not used	Not used	Not used
pre influenza infection levels	Not used	Not used	Not used	Not used	Not used	93
Oxysat record < pre-influenza level at any moment during the day	Not used	Not used	Not used	Not used	Not used	yes
sustain >94% Oxy sat (VSOXYSAT)	N' missing or 'NA'	N' missing or 'NA'	N' at any time during the day	Missing or NA	YES	Not used
Oxysat record <94% at any moment during the day	Not used	Not used	no	yes	yes	Not used

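### Attachment 6 departs from the stated Day 6 primary scale in two limited situations: a not-ready flag on the day of discharge, and declined ventilation

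*SAP*

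**What the plan says.** **Discharge.** The category 1 criterion in Protocol 9.2.1.1 and SAP 5.2.1 is "Discharged from the hospital before the day of assessment", with no readiness condition. For someone who has left hospital, the one stated exception is AMA discharge on the prior day. On the day after such a discharge the SAP says "the subject will be considered as hospitalized", and the score is missing on later days.

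SAP 5.2.1 sends the derivation to Attachment 6. There, the blocks for categories 3 and 2 each contain a route for "day of assessment)=hoendy+1", joined to "RDISHOSP='N' on day(baseline visit) before". If readiness is assessed more than once in a day, any N makes the whole day N. Attachment 6 defines AMA separately: on the day HO shows discharge, "the investigator indicated he is not ready and his SS status is discharged". Of its eight worked examples it states: "Only in case 4 above we have a discharge against medical advice which would lead to missing values from day 8 onwards".

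**Declined care.** The protocol's footnote to the scale reads "If a subject declines medically-indicated mechanical ventilation or care that requires an ICU level of intervention, the subject will be categorized" by the care that would otherwise have been given that day. SAP 5.2.1 carries over the AMA part of that footnote but not this part. Category 5 in Attachment 6 needs a dated record of invasive ventilation, "And CMADMDS in ('Through Endotracheal tube' 'Through Tracheostomy tube' or 'Through ECMO".

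**The concern.** The code that produces the primary endpoint does not reproduce the definition it is meant to implement. Two programmers, one working from SAP 5.2.1 and one from Attachment 6, could give the same subject different Day 6 scores.

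The first departure depends on when a form is filled in. Readiness is assessed once daily, and the Time and Events Schedule fixes no hour. A subject marked not ready on the morning of Day 5 and discharged that afternoon can score 2 or 3 on Day 6. The same subject has already had the event for time to hospital discharge, a confirmatory secondary endpoint, and is out of hospital for the incidence of not being hospitalized on Day 6.

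The second departure scores some of the sickest subjects better than the protocol intends.

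If the conflict is settled only after treatment codes are known, the choice between definitions of the primary endpoint is open to the charge of being data-driven.

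**Working it through.** **1. Attachment 6 set against the stated definition.** In every worked example HO shows discharge on Day 6 and Home on Day 7.

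| Case | Readiness, Day 6 | SS status, Day 6 / Day 7 | AMA | Attachment 6, Day 7 | Stated definition, Day 7, if HO governs |
|---|---|---|---|---|---|
| 1-3 | Not ready | Hospitalized / discharged | No | >1 | 1 |
| 4 | Not ready | Discharged / blank | Yes | >1 (missing from Day 8) | >1 by the AMA exception |
| 5 | Ready | Discharged / blank | No | Home | 1 |
| 6-7 | Ready | Hospitalized / discharged | No | Home | 1 |
| 8 | Blank | Blank (discharged on Day 5) | No | Home | 1 |

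Coding the post-discharge route literally gives the printed Day 7 result in all eight cases. Cases 1-3 depart from the stated definition. The same rule reaches the primary endpoint when the HO record ends on Day 5 with readiness N that day. In Case 8 a blank readiness entry on the HO discharge day leads to Home, so a blank and an N separate subjects whom HO places equally at home.

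**2. Declined ventilation.** Declined ICU care can be captured on the ward: category 4 accepts the REQICU or REASICU flag. Category 5 has no matching flag. The note that types of ventilation may be extended after medical review adds types, not a marker for ventilation that was declined. The best match to the protocol rule that the code can give is therefore category 4.

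**3. The plan's own sample size.** Inputs from Protocol 11.3 and SAP 1.4: placebo 30/30/25/5/5/5%, common odds ratio 0.62 (a 38% reduction), two-sided 5%, 90% power, 1:1. Applying 0.62 to the cumulative odds gives 40.9/29.9/19.4/3.4/3.3/3.2% on pimodivir. The Whitehead formula, with p̄ᵢ the mean of the two arms in category i, is

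N = 12(z₀.₉₇₅ + z₀.₉₀)² / [(ln OR)²(1 − Σp̄ᵢ³)] = 12 × 10.507 / (0.2285 × 0.9175) = 601.4.

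This reproduces the stated 600. Power at 600 is Φ(0.478 × √(600 × 0.9175/12) − 1.960) = Φ(1.278) = 89.9%.

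**4. Illustration of the first departure.** The share of category 1 subjects caught is an assumption; the documents give none. That share was moved from category 1 to category 2, the proportional odds model was refitted to the expected proportions, and power was recomputed at 600 in a single-stage analysis.

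| Share moved (placebo / pimodivir) | Category 1 (placebo / pimodivir) | Fitted OR | Power |
|---|---|---|---|
| 0 / 0 | 30.0% / 40.9% | 0.620 | 89.9% |
| 5% / 5% | 28.5% / 38.8% | 0.624 | 89.2% |
| 10% / 10% | 27.0% / 36.8% | 0.627 | 88.5% |
| 20% / 20% | 24.0% / 32.7% | 0.633 | 87.2% |
| 10% / 20% | 27.0% / 32.7% | 0.68 | 74% |
| 20% / 10% | 24.0% / 36.8% | 0.58 | 95% |

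The last two rows show only that the direction is not fixed. Nothing in the documents suggests unequal shares.

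**The case against.** Five points can be made for the plan.

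- **The route is narrow.** A reader might infer that Attachment 6 keeps every ordinarily discharged subject in hospital for an extra day. It does not: Cases 5-7, marked ready on the discharge day, score Home the next day. This stands.
- **Cases 1-3 may not be at home.** Their SS status is hospitalized on Day 6 and discharged only on Day 7. If SS gives the true discharge day, a score above 1 on Day 7 agrees with the stated definition. If SS was completed before an afternoon discharge, it does not. The documents do not say which source governs, so one cannot simply declare Cases 1-3 wrong. But the coded route uses HO and readiness and never consults SS status, so the conflict with the definition remains.
- **The convention looks deliberate.** SAP 5.3.1.1 likewise moves readiness for discharge to the next day when a subject leaves while not ready, and the estimand describes the scale as reflecting where the subject should be. That explains the route but does not authorize it. The scale applies readiness to subjects still in hospital and makes its post-discharge exception only for AMA.
- **A check already exists.** The fundamental hospital recovery scale ignores readiness and is analyzed on Day 6 with the same type of model. It is only a partial check, because it also drops the ICU-need rules, and it does not settle what the primary score is.
- **Declined ventilation is a small matter.** The SAP is to be read with the protocol, and required ICU care includes acute or imminent respiratory failure, so such a subject should be flagged for category 4. This stands against a reader who infers a routine drop of two categories: category 3 would need the ICU flag to be missed as well.

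**Conclusion.** Both departures are real and both can change Day 6 primary scores, but each is limited. The first applies only where the HO record ends the day before assessment, readiness is N on that discharge day, and the discharge is not AMA. The second applies only to subjects who decline indicated invasive ventilation, and it normally costs one category.

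The size is unknown. Under the assumed equal shares of 5-20%, the effect is small: at most 0.013 on the odds ratio (0.633 − 0.620) and 2.7 percentage points of power (89.9 − 87.2). No figure is offered for declined ventilation, because the documents give no refusal rate.

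Two stronger inferences are not supported. One is a serious loss of power: the 74% figure needs an unequal shift that was chosen for illustration, in a trial that is double-blind. The other is that the error always works against pimodivir: that follows only if the shares are similar in both arms. With equal shares and no treatment effect the two distributions stay identical, so no inflation of the type I error is claimed.

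The reason to act is that the primary endpoint has two definitions that can disagree for the same subject, and that this can still be settled blind.

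**What to change.** Before unblinding:

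1. State whether HO or SS governs the discharge day when they differ.
2. In categories 3 and 2, limit the post-discharge route to genuine AMA discharges, identified by a recorded AMA discharge or by blinded review. Attachment 6's own AMA rule (not ready plus SS discharged on that day) is not enough: a subject marked not ready in the morning and properly discharged that afternoon would meet it whenever SS is updated the same day. Bring Cases 1-4 into line with items 1 and 2.
3. If the route is intended for non-AMA discharges, amend the protocol definition and SAP 5.2.1 to say so, and report the Day 6 primary model without the route as a sensitivity analysis.
4. Restore the declined-care sentence in SAP 5.2.1, and add to category 5 invasive ventilation that was medically indicated on that day but declined, identified by blinded medical review or site query.

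The cost is a few lines of derivation and SAP text and a small number of blinded queries. The sample size does not change. Item 3, if chosen, also needs a protocol amendment.
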